### 4.2 Handling of missing data

#### 4.2.1 Handling of missing data for efficacy analysis

Calculation of derived efficacy variables in the presence of missing data is described in individual subsections of [Section 8.1](#). All derived efficacy variables will be calculated using observed data, and any resulting missing data will be handled as described in this section. All nonresponder imputation (NRI) and MI imputation as described below will be performed only for subjects in the FAS for PA0009.

Additional methods for deriving the PASI response in the presence of missing data are described in [Section 4.2.2](#).

For assessments missing during PA0008, which were to be used in PA0009 for reporting maintenance of response, the following approach will be used:

- For summaries of binary data following NRI, the imputed value from the PA0008 database will be used.
- For summaries of non-imputed (OC) data, the assessment will be left as missing.

For all visits in PA0009 (including PA0009 EV), missing values for binary secondary/other efficacy variables (ACR20, ACR50, ACR70, PASI75, PASI90, PASI100, MDA) or values, which cannot be constructed (eg, for ACR either tender joint count [TJC]/swollen joint count [SJC] are missing or >2 out of the 5 remaining core set measures are missing) will be imputed using NRI. For each visit, subjects with missing data or who have dropped out of the study will be counted as nonresponders. This includes any subjects with missing Baseline values. For PASI response, NRI will be implemented only for subjects with BSA  $\geq 3\%$  at PA0008 Baseline.

For missing continuous secondary/other efficacy variables an MI approach will be used. This will be performed for the following endpoints:

- TJC and SJC

- Psoriasis Area and Severity Index (PASI)
  - For PASI the MI model will be restricted to subjects with a BSA affected by psoriasis of  $\geq 3\%$  at PA0008 Baseline. Subjects with a BSA affected by psoriasis of  $< 3\%$  at PA0008 Baseline will be excluded prior to performing the procedure outlined below.
- Patient's Global Assessment of Disease Activity (PGADA)
- Physician's Global Assessment of Disease Activity (PhGADA)
- Patient's Assessments of Arthritis Pain (PtAAP)
- Health Assessment Questionnaire – Disability Index (HAQ-DI)
- CRP
  - For CRP, the rules for handling measurements that are below the limit of quantification should be followed as per [Section 8.1.7](#). Thus, if any imputed values are  $< 0.16\text{mg/L}$ , these will be replaced with  $0.08\text{mg/L}$  prior to any subsequent reporting.
- MASES
  - For MASES, the MI model will be restricted to subjects with a MASES score  $> 0$  at PA0008 Baseline. Subjects with a MASES score of  $0$  at PA0008 Baseline will be excluded prior to performing the procedure outlined below.
- LDI
  - For LDI, the MI model will be restricted to subjects with LDI scores  $> 0$  at PA0008 Baseline. Subjects with LDI scores of  $0$  at PA0008 Baseline will be excluded prior to performing the procedure outlined below.
- DAS28[CRP]
- PsAID-9
- SF-36
  - For SF-36, this will be performed for the Physical Component Summary (PCS) score and Mental Component Summary (MCS) score only.
- HADS-A and HADS-D
  - Incidence of normal HADS-A and HADS-D scores (defined as having HADS-D  $< 8$  and HADS-A  $< 8$  at the same visit) will be derived at each visit using the values for HADS-A and HADS-D obtained after MI

The missing absolute value (not the change from Baseline) will be replaced by one of a set of plausible values, where each value is a Bayesian draw from the conditional distribution of the missing data given the observed data. The basic assumption in MI is that the underlying missing data mechanism is ignorable, eg, the missing data are missing at random.

All MI procedures will be performed using data from both PA0008 and PA0009 such that missing data across both studies will be imputed (in general, only data from PA0009 will be presented in the summary tables, with the exception of the summaries of maintenance of response where all visits in PA0008 and PA0009 will be presented). Any previous imputation

(MI or last observation carried forward [LOCF] or other imputation) performed in PA0008 will not be considered for PA0009 such that the procedure will use OC data only across both studies. Thus, the results presented in the maintenance tables for visits in PA0008 may differ from those previously reported as part of the PA0008 clinical study report.

As the PA0008 Week 48 time point is synonymous with the PA0009 EV time point, this will be incorporated once only into the model.

The SAS® PROC MI procedure will be used for the imputation.

The MI consists of 3 steps:

- The missing data are imputed  $m$  times to create  $m$  complete datasets.
- The  $m$  datasets are summarized.
- The results of the  $m$  summaries are combined into a single result.

The MI method will be applied as follows:

### Step 1

- Create a data set, sorted by treatment group at completion of PA0008, of subjects with observed values and missing values needing imputation. Missing values will be separated into non-monotone (ie, intermittent missing values between completed assessments) and monotone (ie, missing values after the subject dropped out). The procedure will sequentially estimate an imputation model for the efficacy variable at each post-PA0008 Baseline visit where efficacy variables are collected, with PA0008 Baseline, geographic region, and past TNF inhibitor exposure (as collected on the eCRF in PA0008 for past anti-TNF exposure) as covariates, separately for each treatment group at the completion of PA0008.
- Intermittent missing data will be imputed by draws from the imputation model using the Markov-Chain Monte Carlo (MCMC) method with multiple chains and monotone imputing. A total number of imputations will be 100. The seed used for these imputations will be 2017.

Note: All MI procedures described in this SAP will use the same seed.

- The post-PA0008 Baseline values will be specified in chronological order in the imputation model so that the SAS® PROC MI imputes variables from left to right. If a PA0008 Baseline raw value is missing, the study participant will be excluded. The imputation model based on the MCMC method will only allow multivariate normal variables as predictors. Therefore, past TNF inhibitor exposure and geographic region will be re-coded as indicator variables. For past TNF exposure, this will be 0 for no past exposure and 1 for past TNF exposure. Similarly, for region, this will be 1 for subjects from Europe and 0 for all other subjects. The order for the covariates in the model will be as follows: region indicator variable (Europe = 1, North America = 0), past TNF exposure (Yes = 1, No = 0), Baseline value, and visit variables.
- Once the intermittent missing data are imputed, the monotone missing data will be imputed including covariates as defined above, based on the datasets created by the intermittent missing data MI. Since this dataset already has 100 imputed values at each visit, only 1 imputation will be performed.

## Step 2

The dataset with the imputed results for each treatment arm will be combined into 1 complete dataset including each of the 100 imputations. If any imputed value is less than the lower limit of the allowable range for that parameter (as shown in Table 4-1), it will be changed to the lower limit of the range, and similarly for values higher than the allowable range. This dataset will be used to calculate the change from PA0008 Baseline variable where appropriate.

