4.3.2 Efficacy variables

Other efficacy variables are listed below and will be evaluated at scheduled visits in accordance with the schedule of study assessments in [Table 5-1](#).

- ACR20, ACR50, and ACR70 response
- PASI75, PASI90, and PASI100 response
- Minimal Disease Activity (MDA) as defined in [Table 10-3](#)
- Change from Baseline of PA0008 in the Disease Activity Score-28 based on C-reactive protein (DAS28[CRP]) by visit
- Change from Baseline of PA0008 in MASES
- Change from Baseline of PA0008 in the LDI
- Change from Baseline of PA0008 in Psoriatic Arthritis Impact of Disease (PsAID)-9
- Change from Baseline of PA0008 in Short Form 36-item Health Survey (SF-36)
- Change from Baseline of PA0008 in the Hospital Anxiety and Depression Scale (HADS): HADS-Anxiety (HADS-A) and HADS-Depression (HADS-D) scores
- Depression and anxiety status “normal” as defined by HADS-D and HADS-A <8

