9. Subject develops laboratory abnormalities (with or without clinical symptoms) of alanine aminotransferase (ALT) or aspartate aminotransferase (AST) as defined in [Section 6.3.1](#); neutrophils $<0.5 \times 10^9/L$ (neutropenia); lymphocytes $<0.5 \times 10^9/L$ (lymphopenia). Any laboratory value or change judged to be clinically significant by the Investigator should prompt consideration of whether the subject should continue on the investigational medicinal product (IMP). For clarification, laboratory values that are markedly abnormal as per [Table 17-1](#) and [Table 17-2](#) will be flagged to the Investigator and to the medical monitor but do not trigger mandatory withdrawal unless listed above. (Refer to [Section 6.3.1](#) for withdrawal criteria in relation to potential drug-induced liver injury [PDILI].)
10. Subject has active suicidal ideation as indicated by a positive response (“Yes”) to Questions 4 or 5 or to the suicidal behavior questions of the “Since Last Visit” version of the self-rated electronic Columbia-Suicide Severity Rating Scale (eC-SSRS). The subject should be referred immediately to a Mental Healthcare Professional and must be withdrawn from the study.
11. Subjects with a HADS-D score ≥ 15 must be withdrawn. Any subject who develops a HADS-D score of >10 during the study should be referred immediately to a Mental Healthcare Professional for further evaluation and potential withdrawal by the Investigator.
12. Subjects with newly diagnosed inflammatory bowel disease (IBD) or with IBD flares during the study must:
 - Be referred, as appropriate, to a health care professional treating IBD, such as a gastroenterologist
 - Discontinue IMP and be followed-up until resolution of active IBD symptoms

If IBD flares increase in severity or frequency during the study, the Investigator should use clinical judgment in deciding whether the subject should continue in the study and contact the Medical Monitor and UCB study physician to confirm the subject's suitability for continued participation in the study.

All subjects who withdraw from the study due to an AE must be followed until resolution of the event or until the event is considered stable. All subjects who withdraw from the study due to development of a laboratory abnormality must be closely monitored.

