13.8 Handling of dropouts or missing data

Missing binary efficacy variables will be imputed using nonresponder imputation (NRI). In NRI, each subject with missing data or who has prematurely finished the study will be counted as a nonresponder.

For missing continuous efficacy variables, a multiple imputation (MI) approach will be used. In MI, the missing value is replaced by a set of plausible values, where each value is a Bayesian draw from the conditional distribution of the missing data given the observed data.

Non-monotone missing data (ie, intermittent missing data) will be imputed several times with the Markov Chain Monte Carlo (MCMC) method and monotone missing data will be imputed using a monotone regression model. Each set of imputed data will then be summarized and the summaries will be combined into a single inference (Carpenter and Kenward, 2013).

Safety data will not be imputed.

As a sensitivity analysis, the ACR, PASI, LDI, MASES, and MDA efficacy variables will be analyzed based on observed data in addition to a sensitivity analysis based on multiple imputation of ACR component scores and PASI scores for the ACR and PASI response variables, respectively. Subjects with missing data or who have prematurely finished the study will be treated as missing.

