**Table 4–2: Missing data handling**

Variable	Type	Missing data handling approach		
		NRI	MI/MCMC (monotone regression)	OC
ACR20, 50, 70	Responder	P	S a	S
MASES	Continuous		P	S
LDI	Continuous		P	S
PASI75, 90, 100	Responder	P	S a	S
MDA	Responder	P		S
DAS28 (CRP)	Continuous		P	
CRP	Continuous		P	
PsAID-9	Continuous		P	
SF-36 PCS, MCS	Continuous		P	
HADS-A, HADS-D	Continuous		P	
Incidence of normal depression/anxiety status (using HADS)	Responder		P a	
TJC, SJC	Continuous		P	
HAQ-DI	Continuous		P	
PtAAP	Continuous		P	
PGADA	Continuous		P	
PhGADA	Continuous		P	

ACR=American College of Rheumatology 20, 50, 70% response criteria; CRP=high sensitivity C-reactive protein; DAS28(CRP)=Disease Activity Score 28 joint count C-reactive protein; HADS-A=Hospital Anxiety and Depression Scale – Anxiety; HADS-D=Hospital Anxiety and Depression Scale – Depression; HAQ-DI=Health Assessment Questionnaire - Disability Index; LDI=Leeds Dactylitis Index; LLOQ=lower limit of quantification; MASES=Maastricht Ankylosing Spondylitis Enthesitis Index; MCMC=Markov-Chain Monte Carlo; MDA=Minimal Disease Activity; MI=multiple imputation; NRI=nonresponder imputation; OC=observed case; P=primary method; PASI 75, 90, 100=Psoriasis Area and Severity Index 75%, 90% and 100%; PGADA=Patient’s Global Assessment of Disease Activity; PhGADA=Physician’s Global Assessment of Disease Activity; PsAID-9=Psoriatic Arthritis Impact of Disease-9; PtAAP=Patient’s Assessment of Arthritis Pain; S=secondary method;

SF-36 MCS=Short Form 36-Item – Mental Component Summary; SF-36 PCS=Short Form 36-Item – Physical Component Summary; SJC=swollen joint count; TJC=tender joint count.

a Imputation method is applied on continuous data, and response variable is derived from the continuous data based on complete dataset.

In the event that the MI model fails to converge or will not run for other reasons (eg, data issues, data distribution), alternative approaches may be considered including LOCF and /or OC summaries as appropriate. For some efficacy endpoints, these approaches may be planned already as part of the existing analyses or sensitivity analyses, and therefore it may not be necessary in all cases to provide additional summaries.

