One set of summaries will be produced for all of the above parameters using data following NRI (for binary endpoints) or MI (for continuous endpoints) as appropriate, as described in Section 4.2.1. For BSA the summary will be based on OC data only.

For each of the following variables, an additional set of summaries will be produced using OC data:

- ACR
- PASI
- MDA
- MASES
- LDI

For each of the following variables, an additional set of summaries will be produced after the response variables have been derived following MI of components:

- ACR
- PASI

Finally, for PASI, supplementary summary tables will be presented for the following based on the imputation rules described in Section 4.2.2:

- PASI response derived using LOCF
- PASI response derived based on the BSA observed at the corresponding visit

The summary tables for CRP will display the absolute value and ratio to PA0008 Baseline and will contain n, geometric mean (and 95% CI), median, first and third quartiles (Q1 and Q3), minimum and maximum. Any values for the ratio to PA0008 Baseline below 0.01 will be presented as <0.01 in the listing and summary table.

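### Normal HADS status, a binary efficacy variable, is summarised only after multiple imputation although protocol 13.8 requires nonresponder imputation, and SAP 3.10 does not declare the change

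*SAP*

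**What the plan says.** **Protocol.** Section 4.3.2 includes among the other efficacy variables "Depression and anxiety status “normal” as defined by HADS-D and HADS-A <8". Section 13.8 sends missing binary efficacy variables to NRI, under which "each subject with missing data or who has prematurely finished the study will be counted as a nonresponder". It gives MI a separate scope: "For missing continuous efficacy variables, a multiple imputation (MI) approach will be used". No exception is made for HADS status. MI reaches a responder variable in 13.8 only as a sensitivity analysis, for ACR and PASI.

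**SAP.** The list of NRI variables in 4.2.1 covers the ACR, PASI and MDA responses and omits normal HADS status. Under the MI endpoints, the same section says that normal status "will be derived at each visit using the values for HADS-A and HADS-D obtained after MI". Later in 4.2.1 the reported number and percentage are averaged over the imputations. Table 4–2 classes the variable as a responder endpoint, marks MI as primary, and leaves the NRI and observed-case columns empty. Its footnote confirms that the binary status is derived from the completed continuous scores. SAP 3.10, which lists changes to protocol-defined analyses, does not mention this one.

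**The concern.** The other responder endpoints in Table 4–2 (ACR, PASI, MDA) have NRI as their primary method, which gives a subject who has left no credit. Normal HADS status is the exception, and no reason is given. SAP 4.2.1 treats visits after dropout as monotone missing and imputes them, so each such subject adds a fraction of a normal result at every later visit.

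A reader who knows protocol 13.8 would assume that the reported percentage counts dropouts as not normal. It does not, and no NRI figure stands beside it to show the difference. What is at stake is whether that percentage means what the protocol says, over a treatment period of about two years in which dropout accumulates. SAP 3.10 records smaller changes, such as replacing ACR20 by ACR50 in an antibody figure, so its silence here suggests that the switch went unnoticed.

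**Working it through.** The plan states no rate, dropout figure or sample size for this variable, so there is no figure to reproduce. The check has three steps.

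**1. The two rules side by side**

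| | Protocol 13.8 | SAP 4.2.1 and Table 4–2 |
|---|---|---|
| Normal HADS status (binary) | NRI | Derived after MI of HADS-A and HADS-D |
| Subject who has left | Not normal | Share of 100 imputations with both scores below 8 |
| NRI result shown | Yes | No |
| Declared in SAP 3.10 | – | No |

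**2. Size of the difference.** Let p be the proportion normal among observed subjects, d the missing share at a visit, and q the average imputed-normal rate among the missing. On the same denominator:

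- NRI = (1 − d) × p
- MI = (1 − d) × p + d × q
- MI − NRI = d × q, which cannot be negative

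The documents give none of p, d or q. Assumed ranges are d = 10–30%, p = 60–80%, and q from 0.5p to p.

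| d | p | NRI | MI, q = 0.5p | MI, q = p | Difference (points) |
|---|---|---|---|---|---|
| 10% | 60% | 54.0% | 57.0% | 60.0% | 3 to 6 |
| 10% | 80% | 72.0% | 76.0% | 80.0% | 4 to 8 |
| 20% | 70% | 56.0% | 63.0% | 70.0% | 7 to 14 |
| 30% | 60% | 42.0% | 51.0% | 60.0% | 9 to 18 |
| 30% | 80% | 56.0% | 68.0% | 80.0% | 12 to 24 |

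The overall range is 3 points (0.10 × 0.30) to 24 points (0.30 × 0.80). For scale, with 200 subjects (the protocol's maximum), d = 20% and p = 70%, NRI counts 160 × 0.70 = 112 as normal. MI adds 40 × 0.35 = 14 to 40 × 0.70 = 28 more.

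**3. What credit a subject withdrawn for a high score would receive.** Take a last HADS-D of 15 and, as an example, a last HADS-A of 12. Assume group means of 5 and 5.5, SD 4, adjacent-visit correlation ρ decaying as r = ρ^k over k visits, and the two scores imputed independently. Each imputed score then has mean m + r × (last − m) and SD 4 × √(1 − r²).

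With ρ = 0.6 and k = 1:

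- HADS-D: mean 5 + 0.6 × 10 = 11, SD 3.2, P(<8) = 0.174
- HADS-A: mean 5.5 + 0.6 × 6.5 = 9.4, SD 3.2, P(<8) = 0.331
- Both: 0.174 × 0.331 = 0.058

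For ρ from 0.5 to 0.8, the joint probability is about 0.2–12% at the next visit, 4–33% two visits later and 18–51% four visits later. Under NRI it is 0% throughout. The credit starts low because the model uses the high score. It grows only because the assumed correlation decays.

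**The case against.** Several objections stand.

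**SAP 8.3 does not contradict SAP 4.2.1.** A reader might infer that 8.3 independently requires NRI here, because it pairs NRI with binary endpoints and MI with continuous ones. That sentence goes on to qualify itself and refer to 4.2.1, which assigns this variable to MI. The conflict is between protocol and SAP, and a programmer following the SAP has a clear instruction.

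**The missing observed-case summary is not a breach.** Protocol 13.8 limits observed-data sensitivity analyses to ACR, PASI, LDI, MASES and MDA.

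**MI does not ignore the high scores of subjects withdrawn under criterion 11.** Protocol 6.3 requires withdrawal at HADS-D of 15 or more and, for a score above 10, referral with possible withdrawal. It is tempting to conclude that MI declares these subjects normal. But the triggering score is itself a HADS-D observation, HADS is collected at the early termination visit (protocol 8.8 and 8.10), and SAP 3.5 maps that visit to a scheduled one. The score therefore normally enters the imputation model, withdrawal on it is largely compatible with missing at random, and any credit is fractional. Two limits remain. Few subjects above the threshold would have later HADS data to inform the model. Withdrawal under criterion 10 depends on eC-SSRS answers, which are not in the model. Neither can be sized from the documents.

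**MI followed by dichotomising is a recognised method.** NRI labels everyone who leaves as not normal, whatever the reason. The gap d × q is a difference between two rules and does not measure bias in MI. Which rule suits a mood status better is open to judgement. That supports declaring and justifying a change; it does not excuse leaving it undeclared.

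**The endpoint is minor.** Depression is a safety topic of interest in protocol 9.1.3, but adverse events, adjudicated neuropsychiatric events and eC-SSRS results are reported separately, and safety data are not imputed apart from specified rules for adverse event attributes.

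**Conclusion.** The point holds as an undeclared departure from protocol 13.8 with no NRI result shown. On a common denominator the reported percentage can only equal or exceed the NRI figure. The excess is 3 to 24 points under the assumed ranges, and 7 to 14 points at d = 20% and p = 70%. These sizes cover missing data from all causes and rest wholly on assumed inputs. They say nothing specific about subjects withdrawn because of their HADS-D score, who may be few.

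The documents do not support reading this as a contradiction within the SAP, or as evidence that MI turns severely depressed dropouts into normal results. The consequence is confined to the meaning of one descriptive percentage. No hypothesis test, secondary endpoint, sample size or randomised comparison depends on it. Correction is still worthwhile because the direction is known, the protocol rule is explicit, and the remedy is small.

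**What to change.** In SAP 4.2.1, add normal HADS status to the variables imputed by NRI. In Table 4–2, mark NRI as primary for that row and the MI-derived version as secondary, matching ACR and PASI. This restores the rule in protocol 13.8.

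If the sponsor prefers MI as primary, list the change in SAP 3.10 with a reason and report the NRI percentage beside the MI one. An observed-case summary would be a useful option, but the protocol does not require it.

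The cost is an edit to one list and one table row (or one entry in 3.10) and one extra output table. The downside is that the NRI percentage will be lower and will count as not normal some subjects who left for reasons unrelated to mood.

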## 4 STATISTICAL/ANALYTICAL ISSUES

### 4.1 Adjustments for covariates

All multiple imputation (MI) models (see [Section 4.2.1](#)) will include the following covariates:

- Geographic region at PA0008 Baseline (North America, Europe), as defined in [Section 3.8](#).
- Previous (past) tumor necrosis factor (TNF) inhibitor agent exposure in PA0008. The value in the PA0008 database for past anti-TNF therapy (as collected on the eCRF) will be used for PA0009, without additional derivation.

Missing efficacy data will be handled as described in [Section 4.2.1](#). No imputation will be made for missing safety or background data, except as described in [Section 4.2.3](#) and [Section 4.2.4](#).

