### Step 3 (CRP only)

The CRP data will be presented using the geometric mean, 95% confidence interval (CI) for the geometric mean, median, Q1, Q3, minimum and maximum. The change from Baseline will be expressed as the ratio to Baseline in the summaries. The following approach will be applied:

- Following the MI procedure the ratio to Baseline will be calculated for any of the imputed values
- The natural logarithm of the absolute values and of the ratios to Baseline will be calculated
- The logged values will be summarized by treatment, visit and imputation
- The datasets will be combined using PROC MIANALYZE in order to get the mean and 95% CI estimates from the absolute values and ratios to Baseline (based on logged data) across imputations
- The estimates of the mean and 95% CI will be back-transformed to obtain the geometric mean and 95% CI on the original scale
- For the median, Q1, Q3, minimum and maximum the procedure outlined above for the other endpoints will be followed

As a sensitivity analysis, certain efficacy variables will be summarized based on observed data (see [Section 8](#)).

As a further sensitivity analysis for ACR and PASI responses, the response variables will be derived following MI of the individual components for ACR or following MI of the overall PASI score. The ACR and PASI responses will then be derived for each subject and each imputation (where each imputation is performed across all individual components for ACR) and the number and percentage of subjects with each ACR and PASI response in each imputation will be

calculated. The mean value (across imputations) for the percentage of subjects with each ACR or PASI response will be reported.

A similar approach will be followed for the calculation and summary of the number and percentage of subjects with normal HADS scores (defined as having HADS-D and HADS-A <8 at the same visit) based on the HADS-D and HADS-A values after MI.

Primary and sensitivity analyses are summarized in Table 4–2. All summaries presenting data following MI will include only visits from PA0009 EV onwards (although the MI procedure will incorporate data from both PA0008 and PA0009).

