#### **4.2.2 Additional rules for handling missing data for derivation of PASI response**

Supplementary supporting analyses will be performed for the PASI response in order to take into account missing PASI data during the study. PASI data are known to be missing for some subjects/visits due to an error in the original protocol schedule of events which stated that PASI would only be determined at a given visit if the BSA affected by psoriasis at that visit was  $\geq 3\%$ . The protocol was subsequently updated (Amendment 3) to correct the schedule of events such that PASI is assessed at all visits for subjects with BSA affected by psoriasis of  $\geq 3\%$  at PA0008 Baseline.

These supporting analyses will be performed in addition to those described in [Section 4.2.1](#) and will utilize the BSA assessments to provide surrogate information regarding the PASI response. Two different approaches will be used in this regard:

- For any visit where the derived total PASI score is missing the subject will be considered as a PASI responder if the corresponding BSA assessment at the same visit is 0%. A BSA of 0% will therefore be considered to meet the criteria for PASI75, PASI90, and PASI100 responses.
- For any visit where the derived total PASI score is missing, the PASI response will be imputed using LOCF (based on OC data) only if the BSA has not worsened at any interim time point or the current time point compared to the last visit at which both PASI response and BSA were non-missing (including unscheduled/repeat assessments).

For example, if the PASI score is missing at Visit 4 (Week 12), the response (PASI75, PASI90, or PASI100) at Visit 1 EV will be carried forward and used in the summary, if BSA at Visit 4  $\leq$  BSA at Visit 1. If BSA at Visit 4  $>$  BSA at Visit 1, the response will be left as missing.

- If the data at the PA0009 EV are missing the LOCF will be taken from the last available assessment obtained in PA0008 (based on OC data).
- The approach above will be followed regardless of the BSA value at the corresponding visit, ie, if the BSA=0% at the visit, the previous PASI response will be carried forward for each variable (PASI75, PASI90, and PASI100) and may be Yes or No.

For both approaches above, the rules will be applied to PA0009 data only and only for subjects in the FAS. In addition, this will be implemented only for subjects with BSA  $\geq 3\%$  at PA0008 Baseline.

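### The PASI imputation model omits same-visit BSA, the SAP's own stated cause of missing PASI, so the MI sensitivity analysis of PASI75/90/100 leans low

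*SAP*

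**What the plan says.** SAP 4.1 states that all MI models "will include the following covariates": geographic region and past TNF inhibitor exposure. SAP 4.2.1 Step 1 fits the model at each post-baseline visit "with PA0008 Baseline, geographic region, and past TNF inhibitor exposure", separately by treatment group at completion of PA0008. It fixes the variable order as region, then "past TNF exposure (Yes = 1, No = 0), Baseline value, and visit variables". For PASI, the visit variables are the PASI scores across PA0008 and PA0009. BSA appears only as a filter: subjects below 3% at PA0008 Baseline are left out of the PASI model. On the mechanism, the SAP says: "The basic assumption in MI is that the underlying missing data mechanism is ignorable, eg, the missing data are missing at random".

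SAP 4.2.2 then gives a specific cause: "PASI data are known to be missing for some subjects/visits due to an error in the original protocol schedule of events". Under that schedule, "PASI would only be determined at a given visit if the BSA affected by psoriasis at that visit was" 3% or more. Protocol Amendment 3 corrected the rule. The same SAP section adds two supporting analyses at response level. One counts a missing PASI as a response when BSA is 0%. The other carries the last response forward if BSA has not worsened.

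The imputed scores feed a sensitivity analysis in which response is derived "following MI of the individual components for ACR or following MI of the overall PASI score". Table 4-2 makes NRI primary for PASI75/90/100, with MI and observed-case as secondary. SAP Table 2-1 schedules BSA at every visit at which PASI is scheduled.

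**The concern.** Imputation under missing at random is credible only if the model holds what drove the missingness. Here the SAP names the driver, the study collects it, and the model leaves it out. Take two subjects with the same PASI history. The one whose BSA fell below 3% at the visit is more likely to have a missing PASI and is likely to have a lower true PASI. A model without BSA treats them as exchangeable, so it draws values that are too high and response is understated.

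There is also an internal conflict. By formula 13 in SAP 8.1.10, no affected area in any region gives PASI 0. The first rule in SAP 4.2.2 accordingly treats BSA 0% as meeting all three response levels. The planned MI can draw a positive PASI at that same visit and record a nonresponse.

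What is at stake is how useful the MI tables are as a check on NRI for PASI75 and PASI90 at Week 48, which are secondary efficacy variables. The primary safety objective is not touched.

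**Working it through.** **1. No figure to reproduce.** The documents give no PASI response rate, no count of missing PASI and no size for the subset with BSA of 3% or more at PA0008 Baseline. The check sets the predictor list against the stated mechanism and then illustrates the size.

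**2. Exposure of Week 48.** Amendment 3 is dated 11 Dec 2019 (SAP 1). SAP 8.5 says all subjects had completed Week 48 before the pandemic began, and SAP 10.2.4 dates the pandemic 11 March 2020. From 11 Dec to 11 March is 20 + 31 + 29 + 11 = 91 days, or 13 weeks. Only Week 48 visits in that window could have followed the corrected rule. How many fell there is not stated.

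**3. BSA 0%.** With PASI = 0, formula 14 gives 100 × (baseline − 0) / baseline = 100%. All three responses are then met, so any positive imputed value contradicts the observed BSA.

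**4. Simulation.** All inputs are assumptions. One treatment group had 65 subjects, all with baseline BSA of 3% or more (typical BSA 9%, typical PASI 0.75 × 9 + 0.5 = 7.25). PASI at Weeks 12 to 48 was deleted with probability q when same-visit BSA was below 3%, and entry-visit PASI was complete. Imputation was multivariate normal with 10 imputations and a weak ridge prior, clipped to 0–72. There were 40 replicates for q = 0.3 and 0.6, and 12 for q = 0.9 and 1.0. The comparison is the SAP predictors against the same model plus BSA at baseline and at the visits.

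Week 48 PASI75, %:

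| q | PASI missing | True | NRI | Planned MI | MI + BSA |
|---|---|---|---|---|---|
| 0.3 | 25.0 | 76.1 | 53.8 | 68.6 | 71.1 |
| 0.6 | 46.7 | 77.0 | 35.1 | 59.9 | 66.4 |
| 0.9 | 72.3 | 77.2 | 11.8 | 44.4 | 56.5 |
| 1.0 | 79.0 | 77.1 | 7.1 | 38.4 | 49.0 |

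- Planned MI minus truth: −7.5, −17.1, −32.8 and −38.7 points. With BSA: −5.0, −10.6, −20.7 and −28.1.
- PASI90, planned MI minus truth: 47.8 − 52.7 = −4.9; 40.8 − 52.0 = −11.2; 31.6 − 51.4 = −19.8; 27.1 − 50.6 = −23.5. With BSA (49.1, 45.7, 40.9, 35.1): −3.6, −6.3, −10.5 and −15.5.
- PASI100, planned MI minus truth: −1.4, −4.0, −6.2 and −6.5. At q = 0.3, adding BSA made no useful difference (30.5 against 30.7; truth 32.1).
- Mean PASI among the missing: truth 0.6 to 0.7, planned MI 2.6 to 6.4, with BSA 1.7 to 3.4.

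**5. Where the shortfall comes from.** Response rate = NRI rate + (share missing × share of the missing counted as responders). At q = 0.3 the share counted is:

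- truth: (76.1 − 53.8) / 25.0 = 89%;
- planned MI: (68.6 − 53.8) / 25.0 = 59%;
- with BSA: (71.1 − 53.8) / 25.0 = 69%.

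At the typical baseline PASI of 7.25, the PASI75 cut is 0.25 × 7.25 = 1.8. The true mean among the missing (0.6) lies below it and the planned-MI mean (2.6) lies above it.

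**6. A second, simpler simulation.** It used 110 subjects, with Week 48 PASI predicted from baseline and four PA0008 values, and true PASI75 of 73%. The planned predictors gave 68% and 62% when 25% and 50% of visits followed the old schedule. The direction is the same.

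**The case against.** **The SAP already knows the cause and uses BSA.** This is true. SAP 4.2.2 and 8.3 commit to two BSA-based PASI tables, and BSA categories are tabulated by visit. Those tables leave the MI unchanged, though. The 0% rule does nothing for BSA above 0% and below 3%, and the carry-forward rule can keep a nonresponse even at BSA 0%.

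**The model holds each subject's own PASI history.** This stands. A reader might infer that near-clear subjects are filled in only from subjects with more skin disease. The documents do not support that: SAP 4.2.2 speaks of some subjects and visits, and both studies' PASI values enter the model. The simulations included part of this history (entry and PA0009 visits to Week 48 in one, PA0008 values in the other) and bias remained. Neither carried the full visit series.

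**NRI and MI would not agree.** A reader might infer that agreement between them would give false reassurance. The simulation contradicts this. Under this mechanism MI exceeds NRI by 68.6 − 53.8 = 14.8 to 44.4 − 11.8 = 32.6 points, so the two would visibly differ, with MI nearer the truth. What they share is direction.

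**Adding BSA strains the model.** This stands. PASI has 6 PA0008 visits, the entry visit and 10 later visits: 17 post-baseline variables, plus baseline, region and TNF, makes 20. BSA at all 17 visits would make 37, fitted within each group on variables with many zeros, and the SAP already foresees that MI may fail to run.

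**It is a sensitivity analysis in a descriptive extension.** This is correct, and it limits the weight of the point.

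**Conclusion.** The point holds. The PASI imputation model omits the recorded cause of missingness while assuming ignorability. The resulting PASI75/90/100 estimates lean low, by less than NRI, and can contradict an observed BSA of 0%. The direction follows from the mechanism and appeared in every setting run.

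The size is not known. Under the assumptions above, the PASI75 shortfall runs from about 8 points with 25% of Week 48 values missing to about 39 points with 79% missing. Few affected visits would make it small. It applies only to PASI missing because of the schedule error, not to drop-out or missed visits.

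A reader might also infer that adding BSA would largely repair the estimates. That is not supported. It recovered 2.5 to 12.1 points of PASI75 and 1.3 to 9.3 points of PASI90, leaving most of the PASI75 bias in place. Setting PASI to 0 at BSA 0% and the parsimonious form proposed below were not simulated.

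**What to change.** Change the PASI MI only:

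1. Before imputation, set PASI to 0 where the total score is missing and same-visit BSA is 0%.
2. Add same-visit BSA, suitably transformed, as a predictor for the visit being imputed. Use a parsimonious form, such as visit-by-visit regression with BSA at that visit only, so that the by-group model still converges. Where BSA is missing too, keep the planned predictors.
3. Report PASI75/90/100 from this model. State, by visit and group, how many missing PASI values had BSA of 0%, above 0% but below 3%, 3% or more, or missing.
4. Note beside the tables that the PASI–BSA relation is partly extrapolated below 3%, so the bias is reduced but not removed.

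The cost is SAP wording and programming with data already collected. Protocol 13.8 names MCMC for intermittent gaps, so a visit-by-visit regression for those gaps should be listed in SAP 3.10 as a change to the protocol-defined analysis. The remaining risk is model fit in small groups with many zero values.
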